### **11.2.11 End of the Trial**

The end of the trial is defined as the time at which the last patient has completed their last visit in the study. Upon completion of the study, the study drug will no longer be available to the patient but the Investigator can, at their discretion, discuss alternative treatments with the patient.

### **11.2.12 Clinical Study Report**

At the end of the study a full report per requirements of Sponsor and regulatory authorities will be prepared which will include a narrative of the clinical conduct and results of the study, a statistical report including a description of the analysis performed, and other documentation as may be appropriate. The report will be in electronic format according to eCTD and ICH formatting standards and guidelines. ANDA summary tables will also be generated. Data sets will be provided in SAS® transport (.xpt) format with appropriate description (Read Me) files as required by FDA.

## CONFIDENTIAL PROTOCOL

A Randomized, Double-Blind, Placebo-Controlled, Parallel-Design, Multiple-Site Clinical Study to Evaluate the Efficacy and Safety of Desoximetasone Topical Spray, 0.15% (Taro Pharmaceuticals, U.S.A., Inc.) in Patients with Mild to Moderate Plaque Psoriasis

---

## CONFIDENTIAL PROTOCOL

A Randomized, Double-Blind, Placebo-Controlled, Parallel-Design, Multiple-Site Clinical Study to Evaluate the Efficacy and Safety of Desoximetasone Topical Spray, 0.15% (Taro Pharmaceuticals, U.S.A., Inc.) in Patients with Mild to Moderate Plaque Psoriasis

### 13.0 APPENDICES

#### 13.1 Appendix A

##### **Total Body Surface Area Calculation**

To calculate the Total BSA the following procedure (Mosteller Formula) should be followed.

Total Body Surface Area (BSA) in meters squared

$$m^2 = ((\text{height (cm)} \times \text{weight (kg)}) / 3600)^{1/2}$$

*Patient's height and weight should preferably be measured in cm and kg however if needed:*

*To convert inches (in) to centimeters (cm) the following conversion should be used*

$$1 \text{ inch} = 2.54 \text{ cm}$$

*To convert pounds (lbs) to kilograms (kg) the following conversion should be used.*

$$1 \text{ lb} = 0.45 \text{ kg}$$

The patient's height and weight should be reported to the nearest cm and nearest 0.5 kg. The BSA should be reported to the nearest second decimal place.

For example a patient who is 68 inches tall and weighs 180 lbs will have a reported BSA of:

$$68 \text{ in} \times 2.54 = 173 \text{ cm}$$

$$180 \text{ lb} \times 0.45 = 81.0 \text{ kg}$$

$$\begin{aligned} \text{BSA} &= \text{SQRT} ((173 \times 81.0) / 3600) \\ &= 1.97 \text{ m}^2 \end{aligned}$$

##### **%BSA Affected**

[figure not shown]
To calculate the %Body Surface Area Affected the “Rule of Nine” will be used.

Body Surface Area affected will be calculated using the standard medical procedure of the “Rule of Nines”. The patient's palm surface of the hand represents approximately one percent of his/her body surface area. Calculate to the nearest whole percentage.

## CONFIDENTIAL PROTOCOL

A Randomized, Double-Blind, Placebo-Controlled, Parallel-Design, Multiple-Site Clinical Study to Evaluate the Efficacy and Safety of Desoximetasone Topical Spray, 0.15% (Taro Pharmaceuticals, U.S.A., Inc.) in Patients with Mild to Moderate Plaque Psoriasis

Part	10-14 year child body % of total	Adult body % of total
Arm	9.5%	9%
Head	12%	9%
Neck	1%	1%
Leg	18%	18%
Anterior trunk	16%	18%
Posterior trunk	16%	18%

To be eligible for inclusion in the study a patient must have a % BSA affected of 5-10%

## **CONFIDENTIAL PROTOCOL**

A Randomized, Double-Blind, Placebo-Controlled, Parallel-Design, Multiple-Site Clinical Study to Evaluate the Efficacy and Safety of Desoximetasone Topical Spray, 0.15% (Taro Pharmaceuticals, U.S.A., Inc.) in Patients with Mild to Moderate Plaque Psoriasis

---

### **13.2 Appendix B**

#### **TOTAL LESION SEVERITY SCORE (TLSS)**

Score	Grade	Erythema	Scaling	Plaque Elevation
0	Clear	No evidence of erythema	No evidence of scaling	No evidence of plaques above normal skin level
1	Almost Clear	Pink discoloration, minimal erythema	Occassional fine scales hardly noticeable	Slight, just discernable elevation above normal skin level
2	Mild	Light red coloration	Slight but definite roughness, fine scale present, no cracking	Discernable elevation above normal skin level upon examination, but not pronounced
3	Moderate	Moderate redness, but not dark	Moderate roughness, somewhat coarse scaling	Definite plaque formation with rounded/sloped edges to plaque
4	Severe	Dark red coloration	Marked roughness, coarse/thick scaling, cracking may be evident	Marked elevation with hard, distinct edges to plaque
5	Very Severe	Very dark red coloration with induration present	Very thick scales covering extensive area, severe cracking/fissures may be evident	Very marked elevation, very hard and sharp edges to plaque

To be considered for inclusion in the study, the Target Lesion must have a minimum plaque elevation score of  $\geq 2$ .

## **CONFIDENTIAL PROTOCOL**

A Randomized, Double-Blind, Placebo-Controlled, Parallel-Design, Multiple-Site Clinical Study to Evaluate the Efficacy and Safety of Desoximetasone Topical Spray, 0.15% (Taro Pharmaceuticals, U.S.A., Inc.) in Patients with Mild to Moderate Plaque Psoriasis

---

### **13.3 Appendix C**

#### **INVESTIGATOR'S GLOBAL ASSESSMENT (IGA)**

To be eligible for inclusion in the study the IGA must be 2 - 3 at baseline.

Score	Category	Description
0	Clear	Plaque: elevation: no evidence of plaque elevation above normal skin level. Scaling: no evidence of scaling Erythema: no redness
1	Minimal	Plaque elevation: very slight elevation above normal skin level, easier felt than seen Scaling : limited amount of very fine scales partially covers some of the plaques Erythema: very few of the plaques are light red
2	Mild	Plaque elevation: slight but definite elevation above the normal skin level, typically with edges that are indistinct or sloped on some of the plaques. Scaling: mainly fine scales, some plaques are partially covered. Erythema: some plaques are light red
3	Moderate	Plaque elevation: moderate elevation with rounded or sloped edges on most of the plaques Scaling: somewhat coarser scales; most plaques are partially covered. Erythema: most plaques are red
4	Severe	Plaque elevation: marked to very marked elevation, with hard to very hard sharp edges on virtually all or all of the plaques. Scaling: coarse, thick scales; virtually all or all plaques are covered; rough surface. Erythema : virtually all or all plaques are bright to dusky red.

## **CONFIDENTIAL PROTOCOL**

A Randomized, Double-Blind, Placebo-Controlled, Parallel-Design, Multiple-Site Clinical Study to Evaluate the Efficacy and Safety of Desoximetasone Topical Spray, 0.15% (Taro Pharmaceuticals, U.S.A., Inc.) in Patients with Mild to Moderate Plaque Psoriasis

---

### **13.4 Appendix D**

#### **PSORIASIS AREA SEVERITY INDEX (PASI)**

The PASI is a composite score based on the severity of three different clinical signs of psoriasis in four different areas of the body multiplied by the percent of that specific body area affected multiplied by a weighting factor.

**Erythema, Induration, Scaling will be evaluated using the severity scale below:**

- 0 = Clear
- 1 = Mild
- 2 = Moderate
- 3 = Severe
- 4 = Very Severe

#### **PASI Score**

The PASI score is calculated as follows:

Head/neck       $(E + I + S) \times \text{Area} \times 0.1$

Upper Limbs       $(E + I + S) \times \text{Area} \times 0.2$

Trunk       $(E + I + S) \times \text{Area} \times 0.3$

Lower Limbs       $(E + I + S) \times \text{Area} \times 0.4$

**PASI SCORE = SUM OF ABOVE 4 REGIONS**

E:      Erythema,

I:      Induration

S:      Scaling

Severity is based on the Investigator's assessment of individual signs and symptoms

0 = none, 1 = mild, 2 = moderate, 3 = severe, 4 = very severe using the definitions above

The % of each body region affected is scored as the variable Area above in the PASI formula. For the 4 body regions (head/neck, upper limbs, trunk and lower limbs) if the:

- Area = 0      if % affected is 0%
- Area = 1      if % affected is 1 to 9%
- Area = 2      if % affected is 10 to 29%
- Area = 3      if % affected is 30 to 49%
- Area = 4      if % affected is 50 to 69%
- Area = 5      if % affected is 70 to 89%
- Area = 6      if % affected is 90 to 100%

PASI Score can be presented to the nearest whole number (no decimals and all numbers should be rounded, 0.5 should be rounded up to the nearest whole number). The minimum score would be 0 and the Maximum Score would be 72.

## **CONFIDENTIAL PROTOCOL**

A Randomized, Double-Blind, Placebo-Controlled, Parallel-Design, Multiple-Site Clinical Study to Evaluate the Efficacy and Safety of Desoximetasone Topical Spray, 0.15% (Taro Pharmaceuticals, U.S.A., Inc.) in Patients with Mild to Moderate Plaque Psoriasis

---

### **13.5 Appendix E**

#### **APPLICATION SITE REACTIONS**

The following application site reactions will be evaluated at each visit based on the scale provided below:

Burning

Erosion

Edema

Pain

Itching

Dryness

Absent	0	
Mild	1	(slight, barely perceptible)
Moderate	2	(distinct presence)
Severe	3	(marked, intense)

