## CONFIDENTIAL PROTOCOL

A Randomized, Double-Blind, Placebo-Controlled, Parallel-Design, Multiple-Site Clinical Study to Evaluate the Efficacy and Safety of Desoximetasone Topical Spray, 0.15% (Taro Pharmaceuticals, U.S.A., Inc.) in Patients with Mild to Moderate Plaque Psoriasis

---

for the treatment of plaque psoriasis. Topical application of high potency steroids at the recommended dosing levels are usually well tolerated in all populations, with less than 2% of patients reporting adverse reactions (7% in the pediatric population). The most commonly reported adverse events are burning, stinging, pruritus, and skin thinning/atrophy.

The design for this study is based on results from Phase II dose-ranging and Phase III efficacy studies (NDA # 204141) conducted for Topicort® (desoximetasone) 0.25% topical spray (Taro Pharmaceuticals U.S.A., Inc.). The primary efficacy endpoints (Clinical Success and Treatment Success) are based on these studies as well as those reported in the NDA (# 021835) for the marketed product, Clobex® (clobetasol) 0.05% spray. A sample size estimation of 120 enrolled patients (60 patients per treatment group, 1:1 ratio) is based on the assumption that  $\geq 40\%$  of patients receiving Test (active) treatment, and  $\leq 12\%$  of patients receiving Placebo (vehicle) treatment will have Clinical Success and Treatment Success.

Statistical analyses of the clinical data will be based on FDA guidances and any communications with FDA on how they would like such data analyzed.

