## **CONFIDENTIAL PROTOCOL**

A Randomized, Double-Blind, Placebo-Controlled, Parallel-Design, Multiple-Site Clinical Study to Evaluate the Efficacy and Safety of Desoximetasone Topical Spray, 0.15% (Taro Pharmaceuticals, U.S.A., Inc.) in Patients with Mild to Moderate Plaque Psoriasis

---

active treatment during the study. Nonprescription antipsoriatic shampoos will be allowed during the study when applied solely to the scalp.

8. Patient presents active cutaneous bacterial or viral infection at baseline and/or skin atrophy in ant treatment area.
9. Patient has a history of psoriasis that has been unresponsive to topical corticosteroid therapy.
10. In the Investigator's opinion, the patient has other dermatological conditions, such as atopic or contact dermatitis, that may interfere with the clinical assessments of the signs and symptoms of psoriasis.
11. Patient has a history of allergy or sensitivity to corticosteroids or history of any drug hypersensitivity or intolerance which, in the opinion of the Investigator, would compromise the safety of the patient or the results of the study.
12. Patient has a significant history or current evidence of chronic infectious disease, system disorder, organ disorder or other medical condition that, in the Investigator's opinion, would place the study patient at undue risk by participation in the study.
13. Patient is currently receiving or has received any radiation therapy, anti-neoplastic agents or immunosuppressant medication within 4 weeks before the first dose of study drug.
14. Patient has undergone treatment with any systemic or photo antipsoriatic therapy within 8 weeks of the first dose of study drug.
15. Patient has been treated within 12 weeks (or five half lives, whichever is less) before the first dose of study drug with any biological therapies for psoriasis.
16. Patient has received any systemic steroids within 4 weeks of the first dose of the study drug. The use of inhaled or intranasal corticosteroids is acceptable as long as usage has been stable for at least 2 weeks before the first dose of study drug and will be continued during the study.
17. Females using hormonal contraceptives for less than one complete cycle before entering the study.

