### **9.5.4 Visit 4 (Day 28 ± 2): End of Treatment**

1. **Vital Signs:** The patient's vital signs will be recorded (pulse, blood pressure, temperature and respiration rate).
2. **Dermatological Assessment:** Clinical signs and symptoms of psoriasis will be evaluated by the Investigator based on the following:
  - % BSA assessment (Appendix A)
  - IGA Score (Appendix C)
  - TLSS Score (Appendix B)
  - PASI Score (Appendix D)
  - Application Site Reactions (Appendix E)
3. **Pregnancy Test:** A pregnancy test will be required of all female patients of childbearing potential at the last study visit.

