### **9.6.13 Health Status/Adverse Events**

At Visits 2, 3 and 4 patients will be questioned regarding any changes in their medical status since their previous visit. Any significant changes observed after randomization will be reported as adverse events.

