## **9.7 Adverse Events**

The patients will be monitored throughout the study for any Adverse Events. AEs will be collected through both solicited and unsolicited means and subsequently coded in tabular form using the MedDRA (Version 17 or higher) Adverse Event Dictionary. The patients will be encouraged to report signs, symptoms, and any changes in health to the clinic staff. Severity of each AE will be determined by the staff based on observation and questioning of the patients. The Investigator will judge the relationship of the event to the study treatments. Adverse events should be followed up until they have resolved or stabilized.

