### **10.9 Safety Analysis**

Adverse events (AEs) will be classified using standard MedDRA terminology Version 17.0 or higher and summarized by treatment group. Summary tables comparing the type, incidence, severity will be prepared by treatment group. The relationship of AEs, if any, to the study drug will be assessed by the Investigator. All AEs will be presented

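### Skin atrophy, which the protocol names as a common steroid reaction and excludes at entry, has no item on the graded application-site scale and no scheduled check after baseline

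*Protocol*

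**What the plan says.** - **Expected reactions.** Section 7.3, on high potency topical steroids: "The most commonly reported adverse events are burning, stinging, pruritus, and skin thinning/atrophy". The same paragraph puts adverse reactions of any kind below 2% of patients, with 7% in the pediatric population.
- **Entry.** Exclusion 8 in Section 9.3.2, repeated in the Synopsis: "Patient presents active cutaneous bacterial or viral infection at baseline and/or skin atrophy in ant treatment area".
- **Scheduled local assessment.** Appendix E: "The following application site reactions will be evaluated at each visit based on the scale provided below". Its six items, each scored 0 to 3, are burning, itching, pain, dryness, edema and erosion. Sections 9.5.1 to 9.5.4 schedule it at Visits 1 to 4.
- **Adverse events.** Section 9.6.13: "At Visits 2, 3 and 4 patients will be questioned regarding any changes in their medical status since their previous visit". It adds that significant changes observed after randomization are to be reported as adverse events. Section 9.7: "AEs will be collected through both solicited and unsolicited means and subsequently coded in tabular form".
- **Safety analysis.** Section 10.9, on adverse events: "Summary tables comparing the type, incidence, severity will be prepared by treatment group". Appendix E scores are not mentioned there.

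**The concern.** The protocol treats atrophy as a reaction to expect and as a finding important enough to bar entry. After that it gives no one a scheduled task of looking for it and grading it. Because patients with atrophy in a treatment area are excluded, atrophy seen there later would be new on study, which is what a comparison with vehicle should be able to show.

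Atrophy depends more on a dedicated item than the other named reactions do. It is a sign, it may cause no symptom, and no other Appendix E item overlaps with it. If it is recorded only when an investigator happens to note it, recording may vary between sites and be incomplete. Safety is part of the single study objective in Section 8.0. The population also extends down to age 12, although enrolment of patients aged 12 to 17 waits on safety data from another study (Synopsis and Section 7.5).

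**Working it through.** **1. Matching the Section 7.3 list to Appendix E**

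| Named in Section 7.3 | Item in Appendix E |
|---|---|
| Burning | Burning |
| Pruritus | Itching |
| Stinging | None by name; overlaps with burning and pain |
| Skin thinning/atrophy | None, and no overlapping item |

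**2. Could another scheduled measure record atrophy?**

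- TLSS (Appendix B): plaque elevation bottoms out at 0, no plaque above normal skin level. Skin thinned below that level can still score 0.
- IGA (Appendix C): grade 0 is defined by absence of elevation, scaling and redness. It has the same floor.
- PASI (Appendix D): scores erythema, induration, scaling and area, none of which is thinning.
- Photographs (Section 5.0): target lesion only, at selected sites only.
- Visit 5 (Section 9.5.5): a telephone call, so Visit 4 is the last opportunity to inspect the skin.

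**3. How well does adverse event reporting suit it?** It is available: Section 9.7.1 includes unfavorable signs in the definition, and Section 9.7 has severity judged by observation as well as questioning. The severity grades in Section 9.7.2, however, rest on awareness of a symptom and interference with routine activities. They fit a symptomless sign poorly.

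**4. Illustration of size.** The protocol gives no atrophy rate and no fraction of cases that would be recorded, so there is no plan figure to reproduce on this point. The 89% power in Section 10.2 concerns efficacy and does not enter.

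Inputs:
- n = 60 per arm, the maximum in Section 10.2.
- r = true rate of the reaction in an arm, assumed to be 2% or 7%. These values are borrowed from the Section 7.3 figures for adverse reactions of any kind.
- a = fraction of cases recorded, assumed.

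Formula: P(at least one case recorded in an arm) = 1 − (1 − r × a)^60.

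| a | r = 2% | r = 7% |
|---|---|---|
| 1 | 1 − 0.98^60 = 70% | 1 − 0.93^60 = 99% |
| 0.75 | 1 − 0.985^60 = 60% | 1 − 0.9475^60 = 96% |
| 0.5 | 1 − 0.99^60 = 45% | 1 − 0.965^60 = 88% |
| 0.25 | 1 − 0.995^60 = 26% | 1 − 0.9825^60 = 65% |

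Expected recorded cases at half ascertainment: 60 × 0.02 × 0.5 = 0.6, against 60 × 0.02 = 1.2 with full ascertainment. At 7% they are 2.1 against 4.2.

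Both rates are probably high for atrophy alone, since they cover all adverse reactions. The 7% figure would in any case apply only to the adolescents in an arm.

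**The case against.** The strongest reply is that the skin is already inspected at every clinic visit. The investigator scores %BSA, IGA, TLSS, PASI and application site reactions each time, observed signs are reportable, and Section 10.9 builds the safety profile on adverse events rather than on Appendix E. That stands. It limits the point to the absence of a directed, graded check.

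A reader might go further and infer three things that the documents do not support:

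- **That two of the four commonest reactions go unmeasured.** By name, stinging is missing too. But it is a symptom that patients can report, and it can plausibly be scored under burning or pain. The substance of the gap is atrophy.
- **That the two sections contradict each other.** Section 7.3 is background on a drug class and does not promise that Appendix E covers its list. Appendix E does not claim to be exhaustive. The mismatch is a weak design choice.
- **That the Test versus vehicle safety comparison is thereby lost.** Atrophy stays in that comparison whenever it is reported. A formal test of a rare reaction is out of reach in any case: with 60 per arm, 5 cases against 0 gives a two-sided Fisher p of 0.057, and 6 against 0 gives 0.027. At a 2% rate only 1.2 cases per arm are expected.

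Section 10.9 not naming the Appendix E scores is not part of this point. How they are tabulated may properly sit in the statistical analysis plan, which is not available here.

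**Conclusion.** The point holds in a narrow form. Atrophy is named as a common reaction and screened out at entry, then neither sought nor graded on schedule, and no other scheduled scale can show it. It may be under-recorded. The probabilities above illustrate how a shortfall would act. They do not estimate one, because both the reaction rate and the fraction recorded are assumptions. Nothing here bears on efficacy, power or type I error. This is a worthwhile, low-priority improvement in safety measurement.

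**What to change.** Add a skin atrophy item to Appendix E, assessed at Visits 1 to 4 by the person who already completes the form. Give it its own grade descriptions: the existing ones run from barely perceptible to marked and intense, and are too generic for grading thinning consistently. The Visit 1 entry would also document exclusion 8. Stinging can be added as a separate line or merged into a burning/stinging item.

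The cost is a small CRF change and the drafting of the atrophy grades, with no new visit or assessor. If enrolment is already under way, patients seen before the change will lack the item, and the report should say so.

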## **CONFIDENTIAL PROTOCOL**

A Randomized, Double-Blind, Placebo-Controlled, Parallel-Design, Multiple-Site Clinical Study to Evaluate the Efficacy and Safety of Desoximetasone Topical Spray, 0.15% (Taro Pharmaceuticals, U.S.A., Inc.) in Patients with Mild to Moderate Plaque Psoriasis

---

### **13.6 Appendix F**

#### **Amendments to the Protocol**

Revision	Date	
1	07/29/15	
The following revisions were made to the protocol, Revision 0, dated 02/25/15:
 

• Study schematic was updated to acknowledge that 1 designated site will take photographs of a target area

• The study age range was updated to include patients 12 years of age and older

• Section 7.5 was updated to include justification to begin enrollment in the adult (18 and older) population

• Follow-up phone call (Visit 5) added

• Inclusion Criteria #4 was updated to clarify enrolled of 5-10% BSA affected

• Patient stopping criteria was added to Section 9.7.4

• Section 10.5 was updated regarding the secondary endpoints

• Updates were made to Section 10.6 and 10.7 regarding the Primary and Secondary Analysis

• ITT definition was revised in Section 10.3.1

• PP Population was added in Section 10.3.2

• TLSS scale added (Appendix B)

• PGA scale was updated to an IGA scale (Appendix C)

• PASI scale was added (Appendix D)

• Application Site Reactions were added to the protocol (Appendix E)

Revision	Date	
2	11/04/15	
The following revisions were made to the protocol, Revision 0, dated 02/25/15:
 

• Novum address was updated

• A correction was made to section 9.6.8

• Taro SAE contact information was updated

Revision	Date	
3	01/04/16	
The following revisions were made to the protocol, Revision 2, dated 11/04/15:
 

• Primary efficacy language was updated

• Definition of Clinical Success/Failure and Treatment Success/Failure was updated

Revision	Date	
4	02/24/16	
The following revisions were made to the protocol, Revision 3, dated 01/04/16:
 

• Minor typographical errors were corrected and clarified

